13. SPECIMEN BANKING

- *If specimens will be banked for future research, describe where the specimens will be stored, how long they will be stored, how they will be accessed and who will have access to the specimens*
- *List the information that will be stored with each specimen, including how specimens are labeled/coded*
- *Describe the procedures to release the specimens, including: the process to request release, approvals required for release, who can obtain the specimens, and the information to be provided with the specimens.*

n/a

14. DATA MANAGEMENT AND CONFIDENTIALITY

- *Describe the data and specimens to be sent out or received. As applicable, describe:*
 - *What information will be included in that data or associated with the specimens?*
 - *Where and how data and specimens will be stored?*
 - *How long the data will be stored?*
 - *Who will have access to the data?*
 - *Who is responsible for receipt or transmission of data and specimens?*
- *Describe the steps that will be taken to secure the data during storage, use and transmission.*

The information collected on participants will be derived from self-report, brain MRI/CT scans, and data from study procedures. Brain MRI/CT scans will be obtained either directly from the subject, from the subject's treating physician, or from the subject's file in the health system EMR database with verbal consent from the subject/LAR. After an individual is enrolled into the study, the signed consent form and case report forms will be securely maintained in password protected databases behind the health system firewall and/or in a locked drawer within the locked Feinstein robotics suite, which is only accessible to study investigators. Study data and participant PHI (e.g. demographics, contact info, medical history) will be collected and stored in the HIPAA-compliant system, REDCap. To protect subjects' confidentiality, each subject will be assigned an ID number, and all data will be stored with the subject ID number only and not the subject's name. Any study data containing PHI that is transferred between investigators at Feinstein will be shared via encrypted email, through Syncplicity (health system approved encrypted cloud system server), or through encrypted storage drives. All study data will be stored for at least seven years following closure.

15. DATA AND SAFETY MONITORING PLAN

A specific data and safety monitoring plan is only required for greater than minimal risk research. For guidance on creating this plan, please see the [Guidance Document](#) on the HRPP website.

*Part I – this part should be completed for all studies that require a DSMP.
Part II – This part should be completed when your study needs a Data and Safety Monitoring Board or Committee (DSMB/C) as part of your Data and Safety Monitoring Plan.*

Part I: Elements of the Data and Safety Monitoring Plan

- *Indicate who will perform the data and safety monitoring for this study.*
- *Justify your choice of monitor, in terms of assessed risk to the research subject's health and well being. In studies where the monitor is independent of the study staff, indicate the individual's credentials, relationship to the PI, and rationale for selection*
- *List the specific items that will be monitored for safety (e.g. adverse events, protocol compliance, etc)*
- *Indicate the frequency at which accumulated safety and data information (items listed in # above) will be reviewed by the monitor (s) or the DSMB/C.*
- *Where applicable, describe rules which will guide interruption or alteration of the study design.*
- *Where applicable, indicate dose selection procedures that will be used to minimize toxicity.*
- *Should a temporary or permanent suspension of your study occur, in addition to the IRB, indicate to whom will you report the occurrence.*

Although this is a minimal risk study, to protect both the integrity of the data and the safety of all study participants, study data review in aggregate will occur every 4 months by the Principal Investigator. Additionally, if a subject experiences an adverse event during the course of the study, the PI will be notified immediately and the IRB will be contacted within 5 days if the PI determines that the event is or may be related to the study intervention. If it is determined that the study intervention caused or may have caused the adverse event, the participant may be removed from the study and the study protocol will either be modified or ceased. However serious adverse events are unanticipated as tVNS is a nonsignificant risk device. Additionally, there were no serious adverse device effects of implanted VNS or tVNS in individuals with stroke [8, 41].

Part II: Data and Safety Monitoring Board or Committee

- *When appropriate, attach a description of the DSMB.*
- *Provide the number of members and area of professional expertise.*
- *Provide confirmation that the members of the board are all independent of the study.*

n/a

16. WITHDRAWAL OF SUBJECTS

- *Describe anticipated circumstances under which subjects will be withdrawn from the research without their consent*
- *Describe procedures for orderly termination*
- *Describe procedures that will be followed when subjects withdraw from the research, including partial withdrawal from procedures with continued data collection.*

Study participation is voluntary, and a subject can withdraw at any time by notifying a member of the research team. It is also possible that a subject may be withdrawn from a study without his or her consent. Reasons for such withdrawal may include failure to keep study appointments, changes in medications or medical history such that the subject no longer meets inclusion criteria, experiencing an adverse event that is related or potentially related to the study intervention, or study cessation. Once a subject is withdrawn from the study, no new data will be collected, but previously collected data will be kept and may be used.

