11. RESEARCH PROCEDURES

- *Include a detailed description of all procedures to be performed on the research subject and the schedule for each procedure.*
- *Include any screening procedures for eligibility and/or baseline diagnostic tests*
- *Include procedures being performed to monitor subjects for safety or minimize risks*
- *Include information about drug washout periods*
- *If drugs or biologics are being administered provide information on dosing and route of administration*
- *Clearly indicate which procedures are only being conducted for research purposes.*
- *If any specimens will be used for this research, explain whether they are being collected specifically for research purposes.*
- *Describe any source records that will be used to collect data about subjects*
- *Indicate the data to be collected, including long term follow-up*

Consecutive Sessions of tVNS during robotic therapy intervention

Thirty-six patients with chronic, post-stroke upper extremity hemiparesis will be accepted into this study, and randomized to receive either sham or active tVNS treatment coupled with robotic therapy. There will be 2-3 baseline measurement periods prior to treatment. Following the lead-in period, subjects will participate in a training period consisting of approximately 1 hour sessions robotic therapy paired with tVNS 3x/week for 3 weeks, for a total of 9 sessions. Following the training period, subjects will complete clinical and objective measures both immediately at discharge and again a 3-month follow-up visit.

Lead-in Period

- Week 1, Visit 1 (approximately 90 minutes)
 - Baseline clinical outcome measures
 - Instrumental measures with EMG
 - Medical screening
 - Consent
- Week 1, Visits 2-3 (approximately 60 minutes each)
 - Baseline clinical outcome measures
 - Instrumental measures with EMG

Training Period

- Weeks 2-4, Visits 4-12 (approximately 60 minutes)
 - robotic therapy + tVNS

- Device tolerance questionnaires (every session)

Discharge Evaluation

- Week 4, Visit 13 (approximately 60 minutes)
 - Clinical outcome measures
 - Instrumental measures with EMG

Follow-Up Evaluation

- Week 16, Visit 14 (approximately 60 minutes)
 - Clinical outcome measures
 - Instrumental measures with EMG

**Phase II
Schedule**

	Screen 1	Screen 2	Screen 3	taVNS Tx + robotics	DC eval	3 mo FU
	Visit 1	Visit 2	Visit 3	Visit 4-12	Visit 13	Visit 14
Informed Consent	X					
Medical Hx	X					
Demographic Info	X					
Inclusion Criteria	X					

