tVNS will target the left VNS in order to avoid cardiac side effects associated with right VNS stimulation. The tVNS device will be applied to the left ear using a pair of conductive silicone electrodes, with one electrode contacting the back of the ear and the other electrode on a spring loaded arm, contacting the cymba conchae. Patients will wear the tVNS device for the duration of each 1 hour robotic therapy session. During each session, patients will perform approximately 1000 shoulder/elbow flexion and extension movements and will receive stimulation during only the extensor movements, for a total of 300 stimulations per session. The tVNS current will be delivered during each extensor movement in single 500msec bursts with a frequency of 30Hz and a pulse width of 0.3msec. The current intensity will be individually adjusted to a level just below the patient's reported pain threshold, with amplitudes ranging from 0.1-5.0mA in steps of 100 μ A. The FDA guidance for document for powered muscle stimulators (FDA document 2246) specifies a maximum power density at the electrode site of 250 mW/cm². The MIDI fabricated stimulator has a maximum power density of less than 100 mW/cm², which falls well below the guidance limit for thermal burns. A portable, battery-powered oscilloscope will be used to confirm peak current (for the Roscoe device). These stimulation parameters are similar to parameters that have been demonstrated to be safe in several other tVNS clinical trials [8, 23, 34, 41].

To ensure participant tolerance of stimulation, current will be introduced at the lowest 0.1mA intensity and gradually increased to a level at which the patient just begins to report discomfort, or a maximum of 5mA. The device will then be immediately adjusted to an intensity just below the reported discomfort level, and will remain at this intensity for 10 seconds to confirm patient tolerance. This will be considered the maximum tolerated stimulation intensity threshold for the patient, and stimulation bursts during robotic therapy will then be administered at this level. This tolerability dose will be determined prior to every treatment session for all patients, and recorded in the stimulation tolerance monitoring log. Sham tVNS will have a comparable set-up to active tVNS, with 10 seconds of real current ramping to the maximally tolerated current intensity at commencement,

followed by a slow decrease to no current for the duration of the robotic therapy session.

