Given the rare risk of heart rate changes occurring with tVNS, patients with known cardiac arrhythmias have been excluded from this study. Additionally, subjects will be continuously monitored during therapy. Any patient report of dizziness, lightheadedness, or nausea, which are associated symptoms with arrhythmia will result in immediate reduction in the stimulation intensity and/or cessation of stimulation and robotic intervention. A medical professional trained in basic life support (BLS) and will be present at the time of stimulation and afterwards. Additionally, appropriate medical equipment is available on site and the PI and other trained physicians are available on-call in the case of an emergency to further safeguard against risks.

There are no known risks associated with the use of robotic training for stroke rehabilitation. Some patients have pain in the shoulder after a stroke. Our experience has demonstrated a comparable incidence of shoulder pain in groups that were or were not treated by the robot.

There is also a risk of a breach of confidentiality if unauthorized individuals obtain access to protected health information. This risk will be minimized by securely storing all collected information and limiting access to study investigators only.

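### Section 16 stops all data collection once a subject is withdrawn, so anyone withdrawn during training has no discharge or 3-month outcome

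*Combined protocol and SAP*

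**What the plan says.** Section 16 lists reasons for which staff may withdraw a subject without consent. They include "failure to keep study appointments" and "experiencing an adverse event that is related or potentially related to the study intervention". The rule that follows is: "Once a subject is withdrawn from the study, no new data will be collected, but previously collected data will be kept and may be used". The form's prompt at the head of the section asks for the procedure on withdrawal, "including partial withdrawal from procedures with continued data collection"; the answer gives none.

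Three other places bear on this:

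- Section 15: if the intervention caused or may have caused an adverse event, "the participant may be removed from the study". No other action for the individual subject is named.
- Section 17: symptoms such as dizziness lead to "immediate reduction in the stimulation intensity and/or cessation of stimulation and robotic intervention". The text does not call this a withdrawal and does not say whether assessments continue.
- Section 11: after training, "subjects will complete clinical and objective measures both immediately at discharge and again a 3-month follow-up visit". The schedule puts outcome and instrumental assessments at Visits 1-3, 13 and 14, and none at Visits 4-12.

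Section 12 analyses admission, discharge and follow-up only: a 2x3 ANOVA for EMG and a 2x3 Friedman ANOVA for Fugl-Meyer. It names no analysis set and no handling of missing values.

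**The concern.** For a subject who is withdrawn, Section 16 is a bar on data rather than an omission. It applies even when staff made the decision and the subject would be willing to return. For a subject who only stops sessions, the plan is unclear, because nothing says when stopping becomes withdrawal.

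The loss may depend on treatment. In both arms the current is titrated to discomfort or 5 mA (Section 11: "This tolerability dose will be determined prior to every treatment session for all patients"), and both arms receive the same robotic therapy. After that, only the active arm is stimulated through the session; sham receives a 10-second ramp and a slow decrease to no current. Withdrawals for related events could therefore fall more often on the active arm. If the subjects lost would have done better or worse than the rest, comparing those who remain is biased.

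The planned analyses would usually drop anyone with a missing time point. A better model helps only in part: with just an admission value in the analysis, a withdrawn subject's later outcome rests on assumption. Measuring it uses visits that already exist.

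**Working it through.** **1. The plan's own numbers.** Section 12 wants at least 15 per arm after 10-15% drop-out. At 15%, 30/(1 - 0.15) = 35.3, which rounds up to the stated 36; at 10%, 30/(1 - 0.10) = 33.3, or 34. Expected losses from 36 are 36 × 0.10 = 3.6 to 36 × 0.15 = 5.4. The count of subjects is therefore covered. Comparability of the arms is not.

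**2. What a withdrawn subject contributes.**

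| Withdrawn | Admission | Discharge (Visit 13) | 3 months (Visit 14) |
|---|---|---|---|
| During Visits 4-12 | yes | no | no |
| After Visit 13 | yes | yes | no |

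**3. Difference in exposure.** Section 11 gives 300 bursts of 500 msec per active session: 300 × 0.5 s = 150 s of burst time. After its initial ramp and decrease, sham has none.

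**4. Illustration of size.** These are assumptions, not figures from the documents: 18 per arm, no true effect, and a two-sided 5% two-sample t-test at one time point (not the planned ANOVA). Let kA and kS be the losses in the active and sham arms, and δ the amount in SD by which lost subjects are worse than the rest of their arm.

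- Each arm's remaining mean is too high by δ·k/18, so the bias (active minus sham) is δ(kA − kS)/18.
- Standard error in SD units is √(1/(18 − kA) + 1/(18 − kS)): 0.338 for losses of 1/0 and 0.354 for 3/1.
- The rate of a false result favouring active is the upper tail of a noncentral t with 34 − kA − kS degrees of freedom and noncentrality bias/SE.

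| Losses, active/sham | δ | Bias (SD) | False result favouring active | Two-sided total |
|---|---|---|---|---|
| 1/1 | any | 0 | 2.5% | 5.0% |
| 1/0 | 0.25 | 0.014 | 2.7% | 5.0% |
| 1/0 | 0.5 | 0.028 | 3.0% | 5.1% |
| 1/0 | 1 | 0.056 | 3.6% | 5.3% |
| 3/1 | 0.25 | 0.028 | 3.0% | 5.1% |
| 3/1 | 0.5 | 0.056 | 3.5% | 5.3% |
| 3/1 | 1 | 0.111 | 4.9% | 6.1% |
| 1/0 | −0.5 | −0.028 | 2.1% | 5.1% |
| 1/0 | −1 | −0.056 | 1.7% | 5.3% |
| 3/1 | −0.5 | −0.056 | 1.7% | 5.3% |
| 3/1 | −1 | −0.111 | 1.2% | 6.1% |

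A simulation of 400,000 runs agreed with the upper-tail rates at δ of ±0.5 and ±1 to within 0.0004. The 3/1 case uses 4 losses, about the whole planned drop-out, so it is an upper illustration. At least 15 subjects remain in each arm in every case.

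**The case against.** The strongest objection is that the effect is small and unproven. One net active loss shifts the difference by 0.028-0.056 SD, which is 8-17% of a standard error (0.028/0.338 to 0.056/0.338), and moves the two-sided error only from 5.0% to at most 5.3%. This is a 36-subject pilot without a power calculation. Titration before each session and real-time reduction of intensity (Section 17) should keep related withdrawals few. Withdrawal is discretionary in Sections 15 and 16, and stopping stimulation under Section 17 is not called withdrawal. All of this stands. It limits the weight of the point but does not remove the rule.

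A second objection is that Section 11 also records EMG during tVNS sessions, and Section 16 keeps earlier data. A subject withdrawn in training may thus have some on-treatment EMG that could inform a model. That is fair as far as it goes. It is not a discharge or 3-month value, there is no Fugl-Meyer equivalent, and Section 12 does not use it.

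Third, the remedy will not reach everyone. Subjects withdrawn for missing appointments may not attend Visits 13 and 14, and study cessation may leave no visits to attend. The gain is mainly among those withdrawn for adverse events or for changed medication or history.

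Finally, the lack of a missing-data rule in Section 12 affects ordinary drop-out too, whatever Section 16 says. That is true, and is why the change belongs in both sections.

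**Conclusion.** The concern holds. Followed as written, Section 16 loses both post-treatment outcomes for any subject withdrawn during training, and no other section restores them. For subjects who only stop sessions, the fault is a lack of clarity.

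The size cannot be established from the documents. Under the illustrative assumptions, the false-positive rate favouring active lies between 1.2% and 4.9% against a nominal 2.5%, depending on how many subjects are lost, how unevenly, and whether they would have done worse or better. Equal losses with the same δ in both arms produce no bias. The change should be made because it is cheap and because outcomes not collected at those visits cannot be recovered afterwards. A large bias has not been shown. Confidence is medium.

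**What to change.** **Section 16.** Leave the reasons for stopping sessions as they are. Separate stopping sessions from withdrawing consent for data collection. Invite every randomised subject who stops sessions to the scheduled Visits 13 and 14 unless the subject declines, and record the reason for stopping by arm. State the same in Sections 15 and 17, so that stopping stimulation is not read as the end of data collection.

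**Section 12.** Analyse all randomised subjects in their assigned arm with a method that keeps incomplete subjects. For EMG, use a likelihood-based mixed model for repeated measures with arm, time and arm-by-time. For Fugl-Meyer, use the same model or a rank-based longitudinal method that accepts missing time points. Add one sensitivity analysis that shifts missing outcomes worse and better by fixed amounts, separately in each arm.

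**Cost.** Protocol and consent wording, and up to two existing visits of about 60 minutes for a few subjects, some of whom will decline. The result then estimates the effect of assignment, including subjects who did not complete nine sessions. The mixed model assumes that missing values are explained by the observed data; the sensitivity analysis tests how far the conclusion depends on that. The sample size does not change.

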12. STATISTICAL ANALYSIS

- *Describe how your data will be used to test the hypotheses.*
- *State clearly what variables will be tested and what statistical tests will be used.*
- *Include sample size calculations.*
- *If this is a pilot study, state which variables will be examined for hypothesis generation in later studies.*

For our primary outcome measure, we will investigate whether tVNS paired in a closed loop with robotic therapy changes peak amplitude EMG activation in muscle groups along the shoulder and elbow. We hypothesize that upper extremity flexor synergy will be significantly improved when active tVNS is applied during extensor movements as compared to a sham condition, and will lead to an increase in EMG peak activation at the triceps brachii (elbow extensor muscle). This will be examined with a 2x3 ANOVA with condition (active stimulation vs. sham) and time (peak amplitude of EMG activation during extensor movements at admission, discharge, and follow-up) as factors.

For our secondary outcome measure, we will test whether active tVNS during extensor movements paired in a closed loop with intensive robotic intervention (9 sessions) significantly improves upper extremity motor function as compared to sham tVNS paired with intensity-matched robotics. This will be examined with a 2x3 Friedman ANOVA with condition (active vs. sham tVNS) and time (upper extremity fugl meyer score at admission, discharge, and 3 month FU) as factors.

Since this is a pilot study, there are presently no data from which we can derive a power calculation. However, we propose to enroll 36 subjects, in order to achieve a target of at least fifteen subjects per treatment group and also allow for a 10-15% drop out rate. In our extensive past experience with upper limb hemiparesis rehabilitation studies, 10-15 subjects per treatment group is required at minimum to capture a measurable treatment response. Additionally, two other early pilot studies investigating post-stroke upper limb motor rehabilitation combined with VNS found a significant improvement in motor performance with nine and fourteen subjects per treatment group (e.g. sham and active VNS), respectively [8 & 41].

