17. RISKS TO SUBJECTS

- *Describe any potential risks and discomforts to the subject (physical, psychological, social, legal, or other) and assess their likelihood and seriousness and whether side effects are reversible. Where appropriate, describe alternative treatments and procedures that might be advantageous to the subjects.*
- *Include risks to others, like sexual partners (if appropriate)*
- *Discuss why the risks to subjects are reasonable in relation to the anticipated benefits and in relation to the importance of the knowledge that may reasonably be expected to result.*
- *Describe the procedures for protecting against or minimizing any potential risks, including risks to confidentiality, and assess their likely effectiveness.*

Transcutaneous vagus nerve stimulation by the ear has the potential to cause temporary changes in hearing, pain at the site of stimulation, skin irritation or burns, and in rare occurrences, increases or decreases in heart rate as a result of activating the cervical vagus nerve via transcutaneous electrical stimulation of the ear. However, serious adverse events are unanticipated with tVNS, as there were no serious adverse device effects of implanted VNS or transcutaneous VNS in individuals with chronic stroke [8, 41].

Ear pain/discomfort occurs from stimulation of the sensory nerves innervating the ear. Activation of the sensory nerves correlates with the peak charge density applied to the innervated area. Consequently, during the stimulation period, we will monitor for discomfort and can adjust the charge intensity in real time to rapidly reduce the stimulation intensity and reduce the physical discomfort. This physical discomfort is not serious and the side effects are reversible.

Thermal burns at the stimulation site are due to excess power density through the electrode area. The FDA guidance for document for powered muscle stimulators (FDA document 2246) specifies a maximum power density at the electrode site of 250 mW/cm². The MIDI fabricated stimulator has a maximum power density of less than 100 mW/cm², which falls well below the guidance limit for thermal burns. A portable, battery-powered oscilloscope will be used to confirm peak current for the Roscoe device, and ensure that power density does not exceed this level.

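### Removing a patient for a possibly treatment-related adverse event ends outcome collection, so a removal during training loses both post-treatment assessments

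*Combined protocol and SAP*

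**What the plan says.** Section 16 lists the grounds on which a patient can be withdrawn without consenting to it. One is "experiencing an adverse event that is related or potentially related to the study intervention". The section closes with the rule that applies after any withdrawal: "Once a subject is withdrawn from the study, no new data will be collected, but previously collected data will be kept and may be used". Section 15 has a second removal clause: if the intervention is judged to have caused, or possibly caused, an adverse event, the participant may be taken out of the study. Both clauses are permissive.

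Section 17 describes milder responses. For ear discomfort, "we will monitor for discomfort and can adjust the charge intensity in real time". A report of dizziness, lightheadedness or nausea "will result in immediate reduction in the stimulation intensity and/or cessation of stimulation and robotic intervention". Section 17 does not say whether a patient whose stimulation has stopped stays in the study for later assessment.

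Section 12 analyses two outcomes, each at three time points. The primary is "peak amplitude of EMG activation during extensor movements at admission, discharge, and follow-up"; the secondary is "upper extremity fugl meyer score at admission, discharge, and 3 month FU". The Section 11 schedule marks clinical and instrumental assessments at Visits 1-3, 13 and 14, and none at training Visits 4-12, the only visits with stimulation.

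The form's prompt for Section 16 asks for withdrawal procedures, "including partial withdrawal from procedures with continued data collection". The sponsor's answer gives none.

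**The concern.** A patient who has trouble with the intervention may be told to stop it. Whether that patient is still measured is a separate decision. Sections 15 and 16 join the two: the response they offer to a possibly related event is removal from the study, and removal ends measurement. Outcomes would then be missing because of something the treatment may have done, and no later analysis can recover values that were never collected.

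The loss could plausibly be uneven between arms. Under Section 11, active patients receive bursts with extensor movements during the session. Sham patients receive a brief ramp to the tolerated level, after which the current falls to none. Any imbalance would weaken the comparison that randomisation is meant to protect, and with arms this small each patient carries visible weight.

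**Working it through.** **The plan's own allowance for losses.** Section 12 aims for at least 15 patients per group, 30 in total, with 10-15% drop-out, and enrols 36.

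- At 15%: 30 / (1 - 0.15) = 35.3, rounded up to 36. This reproduces the stated figure.
- At 10%: 30 / (1 - 0.10) = 33.3, rounded up to 34.
- Section 11 tells patients the chance of either condition is 50-50. Taking equal arms, 36 / 2 = 18 per arm, so an arm can lose 18 - 15 = 3 patients and still meet its target.

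This allowance covers how many patients are lost. It says nothing about which patients, or whether the reason for loss depends on treatment.

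**What one removal costs.** Planned values per patient in the Section 12 analyses: 2 outcomes x 3 time points = 6. Training visits: 12 - 4 + 1 = 9.

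| Time of removal | Time points lost per outcome | Values lost | Analysed values left |
|---|---|---|---|
| During Visits 4-12 | 2 of 3 (discharge, 3 months) | 2 x 2 = 4 of 6 | Admission only |
| After Visit 13 | 1 of 3 (3 months) | 2 x 1 = 2 of 6 | Admission and discharge |

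Stimulation is confined to Visits 4-12, so an event during stimulation that leads to prompt removal falls in the first row. Such a patient contributes nothing to either analysis on change after treatment. Section 11 also describes EMG recording during stimulation sessions, and Section 16 keeps data already collected, so some in-training EMG may exist. It is not one of the Section 12 time points and does not replace the discharge or 3-month value.

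**Share of an arm.** 1 / 18 = 5.6% per removed patient. This is a share of patients, not a bias.

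**What cannot be computed.** A bias figure would need a removal rate in each arm and the outcomes that removed patients would have had. The documents give neither.

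**The case against.** The strongest reply is that the rule reaches only patients who are actually withdrawn. Section 17 answers symptoms by lowering or stopping stimulation, not by removing the patient. Section 11 states in general terms that subjects complete assessments at discharge and at 3 months. On that reading, a patient who stops stimulation but is not withdrawn stays on schedule by default. This is fair, and it limits the point to removed patients. It does not help once Section 15 or 16 is used, because the general schedule does not override an explicit stop on data collection, and no criteria say when to remove rather than merely stop stimulation.

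Removals may also be rare. Intensity is set below discomfort before every session in all patients. Current flows for about 300 x 0.5 s = 150 s of an hour's session. Section 11 reports no related serious events in the cited tVNS trials or the team's own studies. Section 15 also says a related event would lead to the protocol being modified or ceased. All of this makes a run of removals less likely. But the trigger is any possibly related event, not only a serious one, and the documents do not give its frequency.

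It is also true that the same stop applies to missed appointments and to changes in medication or medical history, which the fix below does not address, and that analysing patients as randomised does not fill in values still missing. These are limits of the remedy, not reasons to leave the adverse-event route as it is.

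A reader might infer that the treatment comparison will be biased, perhaps in favour of active stimulation. The documents do not support that. Titration to discomfort is common to both arms, so an imbalance is possible but not certain, and nothing is known about how removed patients would have fared.

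**Conclusion.** The point holds in a conditional form. If a patient is removed for a possibly related adverse event during Visits 4-12, following the plan as written leaves only the admission value among the three analysed time points, for both peak EMG and Fugl-Meyer. This follows from an explicit rule read with the visit schedule; it is more than missing detail. The loss is tied to treatment and could differ by arm, and the drop-out allowance does not answer that.

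The size is known only per patient: 4 of 6 analysed values, and 5.6% of an arm if the arms are 18 each. The number of such patients and the size and direction of any bias cannot be derived from the documents, and none is claimed. It would also go too far to say that every patient who stops stimulation is lost, or that a removed patient has nothing beyond baseline. The change is worth making because it is cheap and the outcomes cannot be recovered afterwards.

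**What to change.** - **Sections 15 and 16:** replace removal from the study for an adverse event with discontinuation of stimulation, and of robotic therapy if needed. State that these patients are still assessed at Visits 13 and 14 unless they withdraw consent or assessment would be unsafe. Both sections need the change; amending one leaves a conflicting removal rule in the other.
- **Section 12:** state that these patients are analysed in the arm to which they were randomised.

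The cost is an IRB amendment and, for each affected patient, at most two visits already in the schedule, about 2 x 60 = 120 minutes in total. The change does not oblige anyone to continue stimulation.
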